5.2.1.2.2 Dose Confirmation/Expansion

The objective of dose confirmation in Part B and C is to refine the estimate of the MTD based on TPI design [1] with target toxicity rate $\leq 30\%$. Dose confirmation involves the expansion of at least 1 dose level studied in the dose escalation stage of the study.

Dose confirmation will begin with expansion of the preliminary MTD/MAD identified in the dose escalation stage described in Section 5.2.1.2.1. The dose confirmation part will continue until 20 subjects are studied at the selected dose (combined from dose escalation and dose confirmation) with ≤ 7 of 20 subjects experiencing a DLT. As subjects become evaluable for DLT assessment, the number of subjects who are evaluable for DLT versus the number of subjects who developed a DLT will be continuously assessed. De-escalation and escalation to eligible doses will occur during dose confirmation as shown in [Table 6](#). Escalation or reduction of dose for either agent will be to the next higher or lower dose on MK-1966 being examined in this study, while keeping SD-101 dose fixed. However dose escalation will not exceed 700 mg of MK-1966 or 4 mg of SD-101. Likewise a cohort dose will not be reduced below 70 mg of MK-1966 or 1 mg of SD-101.

Table 6 Dose Confirmation Rules

Number of toxicities	Number of subjects treated at current dose																		
	4	5	6	7	8	9	10	11	12	13	14	15	16	17	18	19	20		
0	S	E	E	E	E	E	E	E	E	E	E	E	E	E	E	E	E	E	
1	S	S	S	S	S	E	E	E	E	E	E	E	E	E	E	E	E	E	
2	D	S	S	S	S	S	S	S	S	S	E	E	E	E	E	E	E	E	
3	DU	D	D	S	S	S	S	S	S	S	S	S	S	S	S	S	S	E	
4	DU	DU	DU	D	D	S	S	S	S	S	S	S	S	S	S	S	S	S	
5		DU	DU	DU	DU	DU	D	D	S	S	S	S	S	S	S	S	S	S	
6			DU	DU	DU	DU	DU	DU	D	D	D	S	S	S	S	S	S	S	
7				DU	DU	DU	DU	DU	DU	D	D	D	D	D	S	S	S	S	
8					DU	D	D	D	D	D	D								
9						DU	D	D											
10							DU												
11								DU											
12									DU										
13										DU									
14											DU								
15												DU							
16													DU	DU	DU	DU	DU	DU	
17														DU	DU	DU	DU	DU	
18															DU	DU	DU	DU	
19																DU	DU	DU	
20																	DU	DU	

E = Escalate to the next higher dose
 S = Stay at the current dose
 D = De-escalate to the next lower dose
 DU = The current dose is unacceptably toxic
 Target toxicity rate = 30%
 Non-informative prior is used: $a=1$; $b=1$;
 $k1=1$; $k2=1.5$; $pow=1$ per {Ji, 2007 #55124}.

Subjects may be enrolled continuously (i.e., without waiting for Cycle 1 completion of subjects who have received the first dose) unless a DLT is observed at the particular dose. Once a DLT is observed, the number of subjects who are enrolled at that dose but are not yet fully evaluable for DLT assessment may not exceed the number of remaining subjects who are at risk of developing a DLT before the dose would be considered unacceptably toxic (denoted as DU in Table 6). For example, if 3/7 subjects have experienced a DLT at a given dose level, no more than an additional 2 subjects should be enrolled at this dose level until additional DLT data are available. This is because this dose level would be considered unacceptably toxic if all 2 of the additional subjects experience a DLT (i.e., 5/9 subjects with DLT in Table 6). To find out how many more subjects can be enrolled, one can count steps in diagonal direction (down and to the right) from the cell (7 subjects, 3 toxicities) to the first cell marked DU.

If enrollment expands to 20 subjects for a dose level, and ≤ 7 of the 20 subjects develop a DLT, then the dose confirmation will stop. If enrollment expands to 20 subjects for a dose level and $>7/20$ subjects develop a DLT, then the next lower dose may be expanded to

further explore the dose-response relationship. Note that while 30% has been the target toxicity rate used to generate the guidelines in [Table 6](#), the observed rate of subjects with DLT at the MTD may be slightly above or below 30%.

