5.2.1.2 Dose Escalation

Enrollment to Arm A, (MK-1966 with SD-101) will begin at the 70 mg for MK-1966 and 1 mg for SD-101. The initial dose combination of SD-101 and MK-1966 will test the tolerability of administering both agents in subjects with advanced tumors. The following three dosing cohorts were chosen with administration of the higher fixed dose of SD-101 to increase immune activation combined with escalating doses of MK-1966. All dose levels in Part A will follow 3+3 design. Dose escalation of MK-1966 will continue to identify a preliminary MTD or MAD.

The dosing for each cohort is as follows:

- 1) 1 mg SD-101 intratumorally and 70 mg MK-1966 intravenously
- 2) 4 mg SD-101 intratumorally and 70 mg MK-1966 intravenously
- 3) 4 mg SD-101 intratumorally and 210 mg MK-1966 intravenously
- 4) 4 mg SD-101 intratumorally and 700 mg MK-1966 intravenously

Note, if the 4 mg SD-101 and 70 mg MK-1966 combination (cohort 2) is not tolerated, then SD-101 will be de-escalated to a 1 mg dose for subsequent cohorts (3 & 4). The study will include up to four dosing cohorts for SD-101 and MK-1966.

5.2.1.2.1 3+3 Dose Escalation

During 3+3 dose escalation, at least 2 days of observation will occur between each of the first 3 subjects at each dose level.

Dose escalation will increase in increments of approximately 3 fold.

The rules applied for the preliminary dose finding using the 3+3 design are as follows:

An initial cohort of 3 subjects is enrolled.

- If 0/3 subjects develops a DLT, escalation to the next dose will occur.
- If 1/3 subjects develops a DLT, another 3 subjects will be enrolled at this dose level.
 - If 0 of the 3 new subjects develops a DLT (for a total of 1/6 subjects with a DLT at this dose level), escalation to the next dose level will occur.

- If ≥ 1 of the 3 new subjects develops a DLT (for a total of $\geq 2/6$ subjects with a DLT at this dose level), the dose escalation stage of the trial will be terminated.

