- If $\geq 2/3$ subjects develop a DLT, the dose escalation stage of the trial will be terminated. If the dose directly below the current dose had been studied in at least 3 subjects, the dose directly below the current dose will be considered the preliminary MTD, and the study will proceed to the confirmation/expansion stage. It is conceptually acceptable to de-escalate to an intermediate, not pre-defined and not previously-studied dose, if evaluation of toxicity at such a dose is desired in lieu of proceeding directly to the dose confirmation/expansion stage of the study. If this approach is taken, 3 new subjects should be enrolled at the new intermediate dose, and the aforementioned rules should be used to determine further enrollment at this dose level.
- If the highest candidate dose of MK-1966 is studied during dose escalation, and 0/3 subjects or $<2/6$ subjects develop a DLT at that dose, then dose escalation will terminate with this finding and this dose level will be taken to the confirmation/expansion stage.

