8.6.2 Statistical Methods for Safety Analyses

Safety and tolerability will be assessed by clinical review of all relevant parameters including AEs, SAEs, laboratory tests, vital signs, ECG measurements and physical examinations.

DLTs will be listed. DLTs and adverse experiences will be summarized as counts and frequencies for MK-1966 in combination with SD-101 dose level that had at least three subjects treated and listed for other dose levels. The estimate of the DLT rate among subjects treated with the RPTD and the 80% Bayesian probability interval with non-informative prior for the estimate will be provided. Laboratory assessments, vital signs, and other safety endpoints will be summarized as appropriate.

In addition, the broad clinical and laboratory AE categories consisting of the percentage of subjects with any AE, a drug related AE, a serious AE, an AE which is both drug-related and serious, and who discontinued due to an AE will be summarized for dose levels with at least 3 subjects treated and listed for other doses. Percentages of subjects in these categories among subjects treated with RPTD and 80% confidence intervals for the estimated percentages calculated using the Clopper-Pearson method will be provided.

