8.6.4 Precision of the DLT rate at RPTD

Since the TPI approach will be used during the dose confirmation/expansion parts B and C, the estimated DLT rate, and its 80% Bayesian Probability Interval (PI) will be calculated from the posterior distribution of the DLT rate at RPTD using the model specified in the TPI approach. If 20 subjects are finally dosed at RPTD during the dose confirmation/expansion stage, the estimated DLT rate and its 80% PI should be similar to one of the rows in [Table 12](#).

Table 12 Precision of the Estimated DLT rates at RPTD

Number of Subjects dosed at RPTD	Number of DLT Events	Estimated DLT Rate	Lower Bound of 80% PI	Upper Bound of 80% PI
20	2	0.10	0.036	0.206
20	3	0.15	0.069	0.267
20	4	0.20	0.105	0.325
20	5	0.25	0.144	0.381
20	6	0.30	0.185	0.435
20	7	0.35	0.228	0.487

Assume non-informative prior distribution of DLT.

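### The plan defines the 20 subjects in the 7-of-20 confirmation criterion in two incompatible ways, and the DLT rate at the recommended dose includes Part A subjects whose low DLT result selected that dose

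*Combined protocol and SAP*

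**What the plan says.** **Criterion.** Section 5.2.1.2.2 runs confirmation "until 20 subjects are studied at the selected dose (combined from dose escalation and dose confirmation) with ≤ 7 of 20 subjects experiencing a DLT", under a stated "Target toxicity rate = 30"%.

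**How a dose gets there.** Section 5.2.1.2.1 sets the Part A rules: "If 0/3 subjects develops a DLT, escalation to the next dose will occur", and a level with one DLT in its first three subjects passes only if the next three have none. The top dose goes forward on the same evidence: if "0/3 subjects or $<2/6$ subjects develop a DLT at that dose, then dose escalation will terminate with this finding". When escalation stops for toxicity, the level below, which has passed, becomes the preliminary MTD.

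**Estimate.** Section 8.6.2 promises "The estimate of the DLT rate among subjects treated with the RPTD and the 80% Bayesian probability interval with non-informative prior". Section 8.5.1 builds the DLT set from all treated subjects with 21 days of observation or an earlier DLT, and does not restrict it to Parts B and C.

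**Planning figures.** Section 8.6.4 introduces Table 12 with "If 20 subjects are finally dosed at RPTD during the dose confirmation/expansion stage". Section 8.6.3.5 gives the number needed to determine the MTD as 32 (12 in Part A plus 20) in Scenario 1 and 44 (24 plus 20) in Scenario 2, reached at 35 and 47 weeks.

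**The concern.** The two sections count different people. Under 5.2.1.2.2, 3 or 6 of the 20 are Part A subjects. Under Section 8, all 20 come after Part A. A decision threshold on the primary endpoint should have one denominator.

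The difference has a direction. The Part A subjects at the dose carried forward are there because few of them had DLTs, so they say little about whether that dose is too toxic. Counting them makes the criterion easier to meet. It also pulls the reported DLT rate down, whatever the true rate is. The plan gives no operating characteristics, no adjustment for this selection and no separate estimate for Parts B and C.

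**Working it through.** **Inputs from the documents.** At most 7 DLTs in 20 and the 30% target (5.2.1.2.2); "Non-informative prior is used: $a=1$; $b=1" (Table 6 notes); a pass in Part A at 0/3 or 1/6 (5.2.1.2.1); 20 subjects each in Parts B and C, one subject enrolled per week, and 3 weeks of observation after the last (8.6.3.5).

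**Assumptions.** The true rate p at the dose is not in the documents; 30% to 45% is shown. All 40 Part B and C subjects are taken as DLT-evaluable and at the recommended dose. Interim Table 6 stops are ignored except where stated.

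**1. Table 12 reproduced.** With a Beta(1+x, 21-x) posterior, the posterior mode is x/20. The 80% highest-density intervals match all six rows (2/20: 0.036 to 0.206; 7/20: 0.228 to 0.487). Equal-tailed intervals do not match, so the highest-density form is used below.

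**2. The two counts.** In Scenario 1 the top dose carries 0/3, so the pooled rule needs 20 - 3 = 17 more: 12 + 17 = 29, against the stated 32. In Scenario 2 it carries 6 subjects, so 14 more: 24 + 14 = 38, against 44. On the plan's accrual the times become 29 + 3 = 32 and 38 + 3 = 41 weeks, against 35 and 47. The totals of 52 and 64 do not change, because each expansion cohort of 20 is planned anyway.

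**3. Effect on the criterion.** With q = 1 - p, a level passes Part A with 0/3 with probability q³ and with 1/6 with probability 3pq⁵. At p = 0.40 these are 0.216 and 0.0933, total 0.309.
- 20 new subjects: P(X ≤ 7 | n = 20) = 41.6%.
- Pooled after 0/3: P(X ≤ 7 | n = 17) = 64.1%.
- Pooled after 1/6: P(X ≤ 6 | n = 14) = 69.2%.
- Weighted: (0.216 × 0.641 + 0.0933 × 0.692) / 0.309 = 65.6%.

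| True rate | 20 new | Pooled |
|---|---|---|
| 35% | 60.1% | 79.6% |
| 40% | 41.6% | 65.6% |
| 45% | 25.2% | 49.5% |

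Including the chance of passing Part A once the level is reached, acceptance at 40% is 0.309 × 0.416 = 12.9% with 20 new subjects and 0.309 × 0.656 = 20.3% pooled. Applying the Table 6 de-escalation boundaries as far as the extracted table is legible, and treating the dose as the highest, widens the 40% comparison to 22.6% against 58.2%. Ignoring the interim stops therefore did not create the gap.

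**4. Effect on the reported DLT rate.** The 8.6.2 set is 40 + 3 = 43 or 40 + 6 = 46 subjects. The expected rate is 40p/43 after 0/3 and (1 + 40p)/46 after 1/6.
- p = 0.30: 27.9% and 28.3%, weighted 28.0%; bias -2.0 points.
- p = 0.40: 37.2% and 37.0%, weighted 37.1%; bias -2.9 points.

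The chance that the highest-density 80% upper bound lies below the truth, by exact enumeration:

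| True rate | Parts B and C (40) | Pooled (43 or 46) |
|---|---|---|
| 30% | 11.1% | 17.0% |
| 40% | 12.9% | 21.1% |

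**The case against.** **Pooling is explicit and usual.** Table 6 is indexed by everyone treated at the dose, which is how a toxicity probability interval design works, and the interval promised is Bayesian with a flat prior, not one with a 10% frequentist tail. That stands, and it is why the in-course decisions should be left alone. It does not settle the conflict with Section 8, and a flat-prior posterior makes no allowance for the selection.

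**If Section 8 governs, the effect on the criterion disappears.** True. A reader might infer that the trial will accept overly toxic doses more often. The documents support that only under the 5.2.1.2.2 count, and they do not say which count prevails.

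**The bias looks larger at n = 20.** There the pooled mean is 25.7% at a true 30% and 33.7% at a true 40%, with upper-bound misses of 18.9% and 26.9%. These describe a snapshot at the confirmation point. Section 8.6.2 covers everyone treated at the recommended dose, so the step 4 figures are the relevant ones.

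**Should the Part B and C estimate replace the pooled one?** A reader might infer so, but it is a trade-off. At a true 40%, the mean squared error is 0.24/40 = 0.0060 for Parts B and C. For the pooled set it is 40 × 0.24/43² + (0.3721 - 0.40)² = 0.0060 after 0/3 and 40 × 0.24/46² + (0.3696 - 0.40)² = 0.0055 after 1/6, weighted 0.0058. Pooled error is lower up to a true rate of 40%, and two-sided coverage is about equal.

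**The bias is not always downward, nor due only to pooling.** If Table 6 escalates to a dose that failed in Part A, that dose carries at least 2 DLTs and pooling raises its rate. The cut-off of 7 also lowers the estimate among accepted doses: at a true 40%, given acceptance, the mean is 34.6% pooled and still only 37.2% from Parts B and C.

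**Conclusion.** The point holds in two parts. First, 5.2.1.2.2 and Section 8 contradict each other on who makes up the 20. The consequence is 32 against 29 and 44 against 38 subjects, and a final-criterion pass probability of 41.6% against 65.6% at a true rate of 40%. Second, the reported DLT rate includes the subjects whose low result selected the dose. The bias is modest, -2.0 to -2.9 points for true rates of 30% to 40%, but the upper bound, which is the safety-relevant end, falls short in 17.0% to 21.1% of trials rather than 11.1% to 12.9%.

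This rests on assumed true rates, on all 40 Part B and C subjects being evaluable at the recommended dose, and on a dose selected by a low Part A result. It does not show that the pooled estimate is invalid or must be demoted. Nor would separate reporting recover the gap between 12.9% and 20.3% acceptance, which depends only on how the 20 are counted.

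**What to change.** 1. Reconcile 5.2.1.2.2 with 8.6.3.5 and 8.6.4, stating in each which subjects make up the 20. Then correct whichever depends on the answer: the 32 and 44 subjects and 35 and 47 weeks in 8.6.3.5, or the premise that introduces Table 12. The choice of count is the sponsor's.
2. In 8.6.2, report the DLT count, rate and 80% interval for DLT-evaluable Part B and C subjects alone beside the pooled estimate. Note that the pooled estimate includes the subjects whose low DLT result selected the dose.
3. Leave the Table 6 decisions unchanged.

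The cost is wording and one table row, with no added subjects. Near a 30% rate the highest-density interval is 0.215 to 0.396 for 12/40 (width 0.181), against 0.220 to 0.395 for 13/43 (0.175) and 0.224 to 0.394 for 14/46 (0.170). The added row's interval is therefore about 3% to 7% wider, and its rate will on average be slightly less favourable.

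### The plan contradicts itself on what follows a Table 6 D or DU at 4 mg SD-101 + 70 mg MK-1966 in dose confirmation

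*Combined protocol and SAP*

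**What the plan says.** **Table 6.** The legend reads "D = De-escalate to the next lower dose" and "DU = The current dose is unacceptably toxic". The second names no action.

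**Section 5.2.1.2.2.** Escalation or reduction, said to be for either agent, goes "to the next higher or lower dose on MK-1966 being examined in this study, while keeping SD-101 dose fixed". The limits follow: at most 700 mg MK-1966 and 4 mg SD-101, and then "Likewise a cohort dose will not be reduced below 70 mg of MK-1966 or 1 mg of SD-101". If 20 subjects are reached with more than 7 DLTs, the section permits expansion of the next lower dose. It does not define that term for a two-drug combination.

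**Section 5.2.1.2.** Cohort 1 is 1 mg SD-101 + 70 mg MK-1966. Cohort 2 is "4 mg SD-101 intratumorally and 70 mg MK-1966 intravenously". Cohorts 3 and 4 keep 4 mg SD-101 with 210 mg and 700 mg MK-1966.

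**Section 5.2.1.2.1.** If a cohort stops escalation, "the dose directly below the current dose will be considered the preliminary MTD", provided at least 3 subjects were studied there. That dose goes into confirmation.

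**Table 5 footnote (Section 5.2), the note in Section 5.2.1.2, and the rationale for the SD-101 dose (Section 4.2.2.2).** If cohort 2 is not tolerated, SD-101 goes to 1 mg. The note applies this to cohorts 3 and 4. The footnote adds Parts B and C.

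**The concern.** Cohort 2 combines the higher SD-101 dose with the lowest MK-1966 dose. It is the one pair for which the cohort list has a lower neighbour (cohort 1) that cannot be reached by changing MK-1966. A rule that moves only MK-1966 has nowhere to go from there.

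The primary objective is to establish an MTD or MAD. If confirmation is running at 4 mg + 70 mg and the DLT count calls for de-escalation, one sentence blocks the move and other passages suggest a change in SD-101. The consequence would then be settled after the toxicity data have been seen, in an open-label trial for which Section 7.1.2.1 plans no external safety reviewer. Section 5.12 pre-specifies no criteria for early termination that could fill the gap.

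**Working it through.** **1. Where D leads if Section 5.2.1.2.2 is applied literally**

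| Current pair (SD-101 / MK-1966) | Destination of D |
|---|---|
| 4 mg / 700 mg | 4 mg / 210 mg |
| 4 mg / 210 mg | 4 mg / 70 mg |
| 4 mg / 70 mg | none |
| 1 mg / 700 mg | 1 mg / 210 mg |
| 1 mg / 210 mg | 1 mg / 70 mg |
| 1 mg / 70 mg | none (lowest pair studied) |

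**2. Whether other text supplies the answer at 4 mg / 70 mg**

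- The Table 5 footnote and Section 4.2.2.2 are triggered by cohort 2 not being tolerated. If confirmation is running at this pair, cohort 2 has already passed the 3+3 rule. Applying the footnote to a later finding would also breach "while keeping SD-101 dose fixed".
- Section 5.2.3.1 lets an individual subject's SD-101 be reduced. It is not a cohort rule.
- The intermediate-dose option in Section 5.2.1.2.1 is an alternative to entering confirmation.

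**3. How the pair is reached**

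Route 1: cohorts 1 and 2 pass 3+3 and cohort 3 (4 mg / 210 mg) fails. Route 2: confirmation starts higher and de-escalates to this pair from 210 mg. Route 2 is not quantified here and adds to the figures below.

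For a true DLT rate p, P(pass 3+3) = (1−p)³ + 3p(1−p)⁵. The first term is passing at 0/3 and the second is passing at 1/6.

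- p = 10%: 0.906
- p = 20%: 0.512 + 0.197 = 0.709
- p = 30%: 0.343 + 0.151 = 0.494, so P(fail) = 0.506
- p = 40%: 0.216 + 0.093 = 0.309, so P(fail) = 0.691
- p = 50%: P(fail) = 0.828

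**4. Chance of D or DU once confirmation starts at this pair**

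Table 6 was rebuilt from its footnote: Beta(1,1) prior, target 0.30, k1 = 1, k2 = 1.5. The interval taken is one posterior SD above the target and 1.5 below, the assignment that fits the printed table. DU is called when P(rate > 0.30) exceeds 0.95. That cut-off is an assumption, because the footnote gives none, but it reproduces the section's example of DU at 5/9. Of 130 readable cells in the rows for 0 to 7 toxicities, 125 match. The other five sit at boundaries of a table whose columns may be damaged in the available text, so they are not treated as errors.

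An exact subject-by-subject binomial recursion starts from the Part A result (which counts toward the 20), treats E as staying, and stops at the first D or DU:

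| True rate at 4 mg / 70 mg | From 0/3, by n = 20 | From 1/6, by n = 20 |
|---|---|---|
| 20% | 0.036 | 0.028 |
| 30% | 0.176 | 0.140 |
| 40% | 0.452 | 0.373 |

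These include the look at n = 20. Stopping at n = 19, the 30% figures are 0.160 and 0.121. With the printed cells in place of the rebuilt ones, the 30% figures by n = 20 are 0.165 and 0.132.

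**5. Joint chance by route 1**

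P = P(cohort 1 passes) × [P(cohort 2 at 0/3) × h₀ + P(cohort 2 at 1/6) × h₁] × P(cohort 3 fails), where h₀ and h₁ are the step 4 values.

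- 10/20/30%: 0.906 × (0.512×0.036 + 0.197×0.028) × 0.506 ≈ 0.011
- 10/30/30%: 0.906 × (0.343×0.176 + 0.151×0.140) × 0.506 ≈ 0.037
- 10/30/40%: 0.906 × (0.343×0.176 + 0.151×0.140) × 0.691 ≈ 0.051
- 10/40/50%: 0.906 × (0.216×0.452 + 0.093×0.373) × 0.828 ≈ 0.099

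**The case against.** The strongest reply is that the documents do address intolerance of this pair: the Table 5 footnote names 1 mg SD-101 for Parts B and C. A reader might therefore infer from Section 5.2.1.2.2 alone that the plan is silent, and that goes too far. What the footnote does not do is settle the matter. Its trigger is a cohort 2 result, and using it in confirmation contradicts the sentence that holds SD-101 fixed. The outcome is a conflict between passages.

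It can also be said that the 1 mg floor merely restates the SD-101 range in the study, since the fixed dose in Parts B and C may be 4 mg or 1 mg. That is a possible reading of the floor. It leaves the reference to either agent unexplained and still gives D no destination.

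On size, a reader might take 0.506 for cohort 3 failing at 30% and set it beside 0.452 for a 40% rate at cohort 2, and conclude that the problem is likely. Those two rates together would need DLT risk to fall as MK-1966 rises with SD-101 unchanged, and the steps have to be multiplied. The joint figures are far smaller.

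Finally, nothing in the text directs continued dosing after DU, and the sponsor and investigators review safety continuously. Both points stand. They limit the harm but do not supply the missing rule. At n = 20, 8 or more DLTs also fall under the separate provision for more than 7 of 20, which is permissive and leaves the lower dose undefined.

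**Conclusion.** The plan is wrong as written on this point. A prescribed Table 6 action cannot be carried out at 4 mg + 70 mg under Section 5.2.1.2.2, and the passages that touch the same situation disagree on whether SD-101 may change. For DU the gap is wider, because the legend names no move at any dose.

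The affected state is reachable but uncommon: about 1% to 10% by route 1 over the four assumed rate patterns. Given a start at this pair with a true rate of 30%, the chance is 0.18 from 0/3 and 0.14 from 1/6, counting the look at n = 20. These figures rest on assumed DLT rates, the assumed 0.95 DU cut-off, a decision after each subject, and E treated as staying. The contradiction itself rests on the text alone. It takes effect when the combination proves toxic, which is when a first-in-human decision rule most needs a single answer.

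**What to change.** Reconcile the SD-101 dose rationale in Section 4.2.2.2, the Table 5 footnote in Section 5.2, the cohort note in Section 5.2.1.2, and Section 5.2.1.2.2 with Table 6 and its provision for more than 7 of 20. The amended text should:

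- agree throughout on whether SD-101 can change during dose confirmation;
- say what a lower or higher dose means for the combination;
- give a D, and a DU, at 4 mg SD-101 + 70 mg MK-1966 one stated consequence;
- say whether the cohort 2 contingency in the Table 5 footnote applies only to the Part A result or also to findings in Parts B and C.

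This should be fixed before Parts B and C open. Which dose or action applies is for the sponsor to decide. The cost is a few sentences and a note to Table 6, with no extra subjects.
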